6.2.4 PREPARATION

Study Drug Application:

Study drug should be removed from freezer 15 minutes prior to application and allowed to thaw at room temperature.

Subjects' dose will be PI-administered at 0H study visit after samples have been procured for engraftment assay. Administers of study drug should wash their hands and wear non-powdered nitrile gloves for application. Subjects will wash their face with Cetaphil® right before in-office application, on Day 1.

6.3 MEASURES TO MINIMIZE BIAS: RANDOMIZATION AND BLINDING

This is an open-labeled, sequential, single-ascending dose study. No randomization or blinding

procedures will be performed.

6.3.1 CONCOMITANT THERAPY

Subjects are excluded from the trial as stated above, if taking any other acne medication. BPO use is only allowed once subjects have been consented to the study and only as part of the Screening period. Subjects are to wait until the end of the study treatment period before initiating any other therapy or investigational agent for the treatment of acne. If, for any reason, the subject must be discontinued from the protocol before the Day 28 visit, the Investigator will make every effort to close out the subject's participation with a final EOS visit before any other acne therapy is initiated.

Use of Other Moisturizers, Sunscreens and Makeup

The use of moisturizers, sunscreens (including moisturizers containing sunscreens) or face makeup is prohibited on the day prior to Day 1 (the last day in the Screening Period) through completion of the Day 3 Visit. Trial participants may continue on, or introduce new moisturizers, sunscreens, or face makeup, after completion of the Day 3 Visit, as long as they do not meet the prohibited medication criteria listed in "Inclusion or Exclusion Criteria" or in protocol section 6.3.1, "Concomitant Therapy" above.

Use of Other Cleansers

The use of cleansers, other than the study-provided Cetaphil®, is prohibited throughout the study, from the Screening Visit to Day 28/EOS.

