4 STUDY DESIGN

4.1 OVERALL DESIGN

This is a first human, single-center, dose escalation, open-label trial of a single application of topically delivered NB01 in subjects with moderate, non-cyclical facial acne.

Ten subjects will be assigned to 1 of 2 dose cohorts in a stepwise fashion after a 5-day pre-treatment with 5.0% daily BPO gel (<https://www.perrigo.com/business/product.aspx?ID=88&let=B> Perrigo 5% BP Aqueous Gel).

- Cohort 1: 10⁵ CFU/cm² NB01
- Cohort 2: 10⁶ CFU/cm² NB01

This will be ascending dose finding whereby 5 initial subjects will be assigned to Cohort 1 to receive a single application of 10^5 CFU/cm² to the facial skin of the nose/cheek. If there are less than 2 dose-limiting toxicities (DLTs) during the 7-day safety assessment, a Dose Escalation Meeting will be held between the PI and the Sponsor Medical Monitor to determine whether Cohort 2 will be opened to enrollment.

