8.2.2 DEFINITION OF DOSE-LIMITING TOXICITIES (DLTs)

Dose-limiting toxicities (DLTs) are defined as AEs occurring during the first 7 days after NB01 application that are not due to the subject's underlying disease, are not clearly attributable to other etiologies, and meet any of the following toxicity criteria:

Dermatologic Toxicities:

- Skin Dryness Score of 3
- Skin Peeling Score of 3
- Irritant/Allergic Contact Score of 3
- Hyperpigmentation Score of 3
- Skin Erythema Score of 3
- Exacerbation of disease determined by an increase in IGA score 1 point beyond baseline screening score

Ocular Toxicities:

- Conjunctival injection score of 3
- Eye irritation score of 3

Mucosal Toxicities:

- Mucosal Irritation Score of 3

If any systemic toxicities develop, the Sponsor will pause the study for further review before proceeding. If 2 or more subjects experience a DLT, or in the event of an SAE that is at least possibly-related to study treatment, the Sponsor will pause the study to discuss with the PI and regulatory authorities, if needed.

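### New facial products are allowed after the Day 3 visit, inside the 7-day DLT window, so a late skin score of 3 can have a rival cause in the Cohort 1 count that gates Cohort 2

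*Combined protocol and SAP*

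**What the plan says.** Section 6.3.1 sets a short restriction on moisturizers, sunscreens and face makeup: their use "is prohibited on the day prior to Day 1 (the last day in the Screening Period) through completion of the Day 3 Visit". After that, "Trial participants may continue on, or introduce new moisturizers, sunscreens, or face makeup, after completion of the Day 3 Visit", provided the product does not fall under the prohibited acne medications. The Day 3 visit is the 48H visit.

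Section 8.2.2 defines DLTs as "AEs occurring during the first 7 days after NB01 application that are not due to the subject's underlying disease", that "are not clearly attributable to other etiologies", and that meet a listed criterion. The criteria include "Irritant/Allergic Contact Score of 3" and "Skin Erythema Score of 3", with the same threshold for dryness and peeling.

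Section 4.1 attaches the gate to this count: "If there are less than 2 dose-limiting toxicities (DLTs) during the 7-day safety assessment", the PI and the Medical Monitor meet to decide whether Cohort 2 opens. Section 8.1 adds that there must be no possibly related SAE. Section 8.2.2 pauses the study if 2 or more subjects have a DLT. Section 10.3 sets 5 DLT-evaluable subjects per cohort.

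**The concern.** The restriction on facial products ends about five days before the safety window does. A subject may put a new moisturizer, sunscreen or makeup on the treated cheek and nose on Day 4 and have an intense contact dermatitis, erythema, dryness or peeling score by Day 7. NB01 and the new product are then both candidate causes. The trial has no concurrent control to help separate them, and no section says how such a score is to be attributed.

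The records may not settle it either. No visit is scheduled between 48H and Day 7, so unless an unscheduled visit occurs, product start and reaction onset are reconstructed at Day 7. The e-diary, as described in the footnotes to 1.2 and in 5.5, covers BPO applications and Cetaphil washes. The concomitant review in 8.1 covers therapies and medications and does not name cosmetics.

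What is at stake is the Cohort 1 DLT count, which decides whether the Dose Escalation Meeting is held or the study is paused. With five subjects, one misclassified event can move the count across the threshold.

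**Working it through.** The plan states no error rate, power or sample-size calculation (10.2), so there is no figure of its own to reproduce. The check has two parts.

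**Overlap of permitted new products with the DLT window**

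- DLT window (8.2.2): 7 × 24 = 168 h after application.
- New products permitted from (6.3.1 and 1.2): the 48H visit, with a window of ±2 h.
- Overlap: 168 − 48 = 120 h, and 120/168 = 71%. With the visit window, 118/168 = 70% to 122/168 = 73%.

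This is permitted time. It is not measured use, and it is not a share of the risk.

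**Sensitivity of the 2-of-5 threshold to over-counting**

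Let p be the probability that a subject has a true DLT. Let q be the probability that a subject has a product-caused score of 3 that is counted as a DLT. Both are assumptions, because the documents give neither. Each subject is counted at most once, and p and q are taken as independent.

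- Effective rate: p′ = 1 − (1 − p)(1 − q).
- P(2 or more of 5) = 1 − (1 − p′)⁵ − 5p′(1 − p′)⁴.

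At p = 0.10 and q = 0: 1 − 0.9⁵ − 5(0.1)(0.9⁴) = 1 − 0.5905 − 0.3281 = 0.081.

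At p = 0.10 and q = 0.05: p′ = 1 − 0.90 × 0.95 = 0.145, and the probability is 1 − 0.4569 − 0.3874 = 0.156.

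| True DLT rate p | q = 0 | q = 0.02 | q = 0.05 | q = 0.10 |
|---|---|---|---|---|
| 0.05 | 2.3% | 4.1% | 7.8% | 15.6% |
| 0.10 | 8.1% | 10.9% | 15.6% | 24.2% |
| 0.20 | 26.3% | 29.6% | 34.6% | 43.0% |

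**Direction of the error**

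The exclusion in 8.2.2 applies only where another cause is clear. If NB01 and a new product cannot be told apart, the other cause is not clear and the event stays in the count. Over-counting is therefore what the text produces by default. Removal requires the investigator to judge that the product is the clear cause.

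**The case against.** The best case for the plan is that the gap is small and partly covered. The first 48 hours are protected, prohibited acne products stay barred, and other cleansers are barred to Day 28. Concomitant medications are reviewed at every visit, and 11.1.11 requires their start and end dates in source. The causality categories in 8.3 weigh other contributing factors. The default error is also the cautious one, since an over-count leads to a pause for discussion. All of this stands. It narrows the gap to two items: cosmetics are not named in any record, and the two dates are not aligned.

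Three stronger readings are tempting, and the documents do not support them.

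- **True NB01 reactions would routinely be lost from the count.** This conflicts with the word *clearly* in 8.2.2. A calculation that removes a fixed share of all DLTs would also remove events from the first 48 hours, when products are barred. It would remove the ocular, mucosal and IGA criteria too, which lie outside this mechanism.
- **One event decides escalation by itself.** Fewer than 2 DLTs leads to a meeting of the PI and the Medical Monitor. Two or more subjects with a DLT leads to a pause for discussion with the PI and, if needed, regulators. Either discussion can examine product history, provided it was recorded.
- **71% of the risk is exposed.** The figure is a share of hours and says nothing about when reactions occur.

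It is also fair to say that aligning the dates would not give a clean attribution. Resumed habitual products remain in use, and BPO, which 2.1 describes as irritating and drying, may end only about 24 hours before dosing.

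**Conclusion.** The concern holds as a modest, avoidable weakness. The permission in 6.3.1 and the window in 8.2.2 overlap by about five days, and within that overlap a late skin score of 3 can have a rival cause in the count used for the first-in-human escalation decision.

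The expected direction is over-counting. Its size cannot be derived from the documents. In the illustration at a true rate of 10%, the chance of reaching the threshold roughly doubles, from 8% to 16%, if 5% of all subjects have a product-caused score of 3 that is counted. At 2% it moves only to 11%. These values of q apply to all subjects, whether or not they start a product. They show how sensitive a 2-of-5 rule is and do not forecast what will happen.

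**What to change.** Reconcile the product-introduction date in 6.3.1 with the 7-day window in 8.2.2, so that elective introduction of new facial products does not overlap DLT evaluation. The sponsor and investigator should set the exact rule, including how it treats sunscreen and any product needed to treat an adverse event. If some overlap is kept, 8.2.2 should state in advance how a score of 3 that follows a new product is attributed.

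Add a line to the concomitant medication form for the name and start date of every facial product used from Day 3 to Day 7. Show these beside any score of 3 at the Dose Escalation call.

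The cost is a wording change, one form line, and a few days' wait for subjects who want to try a new product electively. Resumed products and any exempted sunscreen would remain as rival causes; the log makes them visible but does not remove them.

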7 STUDY INTERVENTION DISCONTINUATION AND PARTICIPANT DISCONTINUATION/WITHDRAWAL

7.1 PARTICIPANT DISCONTINUATION/WITHDRAWAL FROM THE STUDY

Participants are free to withdraw from participation in the study at any time.

Participants will remain in the study through Day 28, or may discontinue early if any of the following criteria are met:

- PI decision
- Subject withdrawal of consent
- Subject is lost to follow-up
- Unacceptable Toxicity (exacerbation of IGA 1 point higher than baseline)
- Sponsor termination of the trial

A PI may discontinue a participant from the study for the following reasons:

- Pregnancy
- Failure to comply with the study procedures, including inability to receive study drug or missing study appointments
- If any clinical AE, laboratory abnormality, or other medical condition or situation occurs such that continued participation in the study would not be in the best interest of the participant
- Disease progression, which requires discontinuation of the study intervention

The reason for participant discontinuation from the study will be recorded on the Case Report Form (CRF)/electronic CRF (eCRF).

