Subject/Study Duration:	Subject participation in the trial will be approximately 5 weeks. Approximately 1 week pre-treatment with a daily 5.0% BPO gel 1 month of study drug: single application and 28-day follow up

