The following will be completed at all office study visits (0H, 6H, 24H, 48H, 7 days, and 28 days), unless otherwise specified:

- Assess for any new or existing AEs or SAEs
- Review concomitant medications
- Obtain cheek samples for
 - Porphyrin presence (Pear 3D)
 - Sebum production (Pear 3D)
- Photography (Pear 3D)
- IGA
- Absolute lesion counts
- pH of skin (pH meter)
- Assess engraftment via Fab-Swab Filtered Air Breathable Sterile Flocked Collection Device (PurFlock® Ultra-Puritan Diagnostics) (TaqMan® assay)
- Assess follicular engraftment via Bioré® strip (TaqMan® assay, at 24H only)
- Urine dipstick pregnancy test (females of childbearing potential, at 0H and Day 28 only)

NOTE: Additional vital signs and CBC may be repeated, as clinically indicated.

End of Study (EOS)

Subjects will remain in the study through Day 28, or may discontinue early, as described in protocol section [7.1](#). Subjects will have completed the study upon conclusion of the Day 28/EOS visit procedures. Subjects who discontinue prior to Day 28 should have the EOS visit scheduled as soon as possible, in

order to complete final safety assessments, prior to discontinuation from the study.

Early Discontinuation of Subjects

Subjects may voluntarily withdraw from the study at any time. A subject's participation in the study may be terminated if it is deemed by the PI or Sponsor that it is unsafe for the subject to continue in the study. Subjects who discontinue prior to completing the DLT evaluation period (i.e., prior to completion of Day 7 procedures) for reasons other than a DLT, will be replaced.

Notification of early subject discontinuation from the study and the reason for discontinuation will be made to Sponsor and will be clearly documented on the appropriate eCRF.

Study Termination

The study may be stopped at his/her study site at any time by the site PI. Sponsor may stop the study (and/or the study site) for any reason with appropriate notification. Both the Sponsor and the PI reserve the right to terminate the study at any time. Should this be necessary, both parties will arrange discontinuation procedures and notify the appropriate regulatory authority(ies), and IRBs. In terminating the study, Naked Biome and the PI will assure that adequate consideration is given to the protection of the subjects' interests.

Adverse Events (AEs)

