The PI must also complete the Serious Adverse Event Report Form, in English, notify the Sponsor and, if necessary, send the completed and signed form to the Sponsor or designee within 24 hours of becoming aware of the SAE. The PI must provide a causality assessment, that is, assess whether there is at least a reasonable possibility that the SAE is related to the study treatment: suspected (yes) or not suspected (no).

Investigational site personnel must report any new information regarding the SAE within 24 hours of becoming aware of the information in the same manner that the initial SAE Report Form was sent. Follow-up information is recorded on an amended or new SAE Report Form, with an indication that it is follow-up to the previously reported SAE and the date of the original report. The follow-up report should include information that was not provided on the previous SAE Report Form, such as the outcome of the event (e.g., resolved or ongoing), treatment provided, action taken with study drug because of the SAE (e.g., dose reduced, interrupted, or discontinued), or subject disposition (e.g., continued or withdrew from study participation). Each recurrence, complication, or progression of the original event should be reported as follow-up to that event, regardless of when it occurs.

The treating PI will determine AEs by:

- Active query for any systemic symptoms
- Limited facial physical examination
- Utilization of Investigator Assessment of Tolerability Scale (0 = None; 1 = Slight; 2 = Moderate; 3 = Intense) for assessment of:
 - Skin Dryness
 - Skin Peeling
 - Irritant/Allergic Contact Dermatitis
 - Hyperpigmentation
 - Skin Erythema
 - Conjunctival Injection
 - Ocular Irritation
 - Mucosal Toxicity
- Assessment of disease status using IGA Score and Acne Lesion Count

Toxicities that warrant subject discontinuation from the trial, as deemed appropriate by the PI, include but are not limited to: ulceration, extreme redness, worsening of acne, extreme skin irritation, extreme ocular irritation, extreme mucosal irritation, extreme contact dermatitis.

REPORTING

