- Possibly Related – There is some evidence to suggest a causal relationship (e.g., the event occurred within a reasonable time after administration of the trial medication). However, other factors may have contributed to the event (e.g., the participant's clinical condition, other concomitant events). Although an AE may rate only as "possibly related" soon after discovery, it can be flagged as requiring more information and later be upgraded to "probably related" or "related", as appropriate.
- Unlikely related – A clinical event, including an abnormal laboratory test result, whose temporal relationship to study intervention administration makes a causal relationship improbable (e.g., the event did not occur within a reasonable time after administration of the study intervention) and in which other drugs or chemicals or underlying disease provides plausible explanations (e.g., the participant's clinical condition, other concomitant treatments).
- **Not Related** – The AE is completely independent of study intervention administration, and/or evidence exists that the event is definitely related to another etiology. There must be an alternative, definitive etiology documented by the clinician.

PREGNANCY

Pregnancy, in and of itself, is not considered as an AE unless there is suspicion that study drug may have interfered with the effectiveness of a contraceptive medication or method. Any pregnancy where the estimated date of conception occurs either prior to the last visit or within 30 days of the last study treatment or exposure to study drug (due to breast feeding) must be reported. When a pregnancy has been confirmed in a subject during maternal or paternal exposure to study drug, the following procedures should be followed to ensure subject safety:

- The study drug must be discontinued immediately (female subjects only and subject must be withdrawn from study).
- The PI must complete and submit the Clinical Trial Pregnancy form to the Sponsor or its designee within 24 hours of learning of the pregnancy.

Data on fetal outcome and breastfeeding are collected for regulatory reporting and drug safety evaluation. Follow-up should be conducted for each pregnancy to determine outcome, including spontaneous or

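### Toxicity or worsening acne can end study participation after the only dose has been given, so reacting subjects may miss scheduled assessments, and section 10.4 does not say how their early end-of-study data are summarised

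*Combined protocol and SAP*

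**What the plan says.** The synopsis (section 1.1) describes the treatment phase as "1 month of study drug: single application and 28-day follow up". Sections 6.1.1 and 8.1 have the investigator apply that one dose at 0H.

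Section 7.1 sets the default and its exceptions: "Participants will remain in the study through Day 28, or may discontinue early if any of the following criteria are met". The listed criteria include "Unacceptable Toxicity (exacerbation of IGA 1 point higher than baseline". A second list, of reasons for which the investigator may discontinue a participant, includes "Disease progression, which requires discontinuation of the study intervention". Section 8.2.1 then introduces a non-exhaustive list, in which worsening of acne appears, as "Toxicities that warrant subject discontinuation from the trial, as deemed appropriate by the PI".

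On what happens next, section 8.1 says: "Subjects who discontinue prior to Day 28 should have the EOS visit scheduled as soon as possible". The Schedule of Events footnote on the EOS visit says the same, and section 6.3.1 seeks that visit before any other acne therapy starts. No section describes a subject who has been dosed, has reacted and remains under scheduled observation as a separate status.

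The Schedule of Events has one combined Day 28/EOS column. Section 10.4.1 summarises data by subject, time point and cohort, with no rule for missing Day 28 data or for EOS data obtained early.

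**The concern.** In a repeat-dose trial, taking a subject off treatment for toxicity protects that subject. Here the single dose is already on the skin when any toxicity can appear, so the same wording protects no one from further dosing. What it can end is observation, and it does so in the subjects who react.

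Safety and engraftment are primary objectives (sections 1.1 and 3), and section 2.2 states that no in vivo safety data exist for this kind of product. The course of a reaction between the first days and Day 28 is therefore information the trial is meant to supply. Exit also depends on an outcome: a 1-point rise in the Investigator Global Assessment (IGA) is an exit criterion, while IGA is a secondary efficacy endpoint. The decision lies with an investigator who is unblinded (section 6.3). At five subjects per cohort (section 10.3), one subject is 20% of a Day 28 summary.

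**Working it through.** The plan gives no figure to reproduce: section 10.2 makes no sample size or power estimate, and no rate of IGA worsening or dropout is stated.

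**Inputs**
- Post-dose visits are at 6H (Day 1), 24H (Day 2), 48H (Day 3), Day 7 and Day 28 (section 1.2).
- IGA, lesion counts and AEs are assessed at each of them. Section 8.1: "The following will be completed at all office study visits (0H, 6H, 24H, 48H, 7 days, and 28 days), unless otherwise specified".
- After the last day of participation, new non-serious AEs are recorded for 7 days and serious adverse events (SAEs) for 30 days (section 8.2.3).
- Entry IGA is Grade 3 on a 0 to 4 scale (section 5.1, Appendix B).
- There are two cohorts of 5 (section 10.3).
- Assumption: the EOS visit takes place on the day of exit and Day 28 falls on its nominal date.

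**Observation forgone**
- Scheduled assessment lost = 28 − exit day.
- Days to Day 28 without recording of new non-serious AEs = 28 − (exit day + 7).
- The same for SAEs = max(0, 28 − (exit day + 30)).

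| Exit visit | Study days lost | New non-serious AEs not recorded | New SAEs not recorded |
|---|---|---|---|
| 6H, Day 1 | 28 − 1 = 27 | 28 − 8 = 20 | 0 (window to Day 31) |
| 24H, Day 2 | 28 − 2 = 26 | 28 − 9 = 19 | 0 (Day 32) |
| 48H, Day 3 | 28 − 3 = 25 | 28 − 10 = 18 | 0 (Day 33) |
| Day 7 | 28 − 7 = 21 | 28 − 14 = 14 | 0 (Day 37) |

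**How often the IGA criterion might be met**

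The documents give no rate, so a range is assumed. The chance of at least one such subject among n is 1 − (1 − p)^n.

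| Assumed p | Cohort of 5 | All 10 |
|---|---|---|
| 5% | 23% | 40% |
| 10% | 41% | 65% |
| 20% | 67% | 89% |
| 30% | 83% | 97% |

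**Effect on a Day 28 IGA summary**

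Assume that k of 5 subjects go from Grade 3 to Grade 4 and stay there, and that the others do not change.
- k = 1: all five observed gives a mean change of +1/5 = +0.2 and 20% worse. Completers only (n = 4) gives 0.0 and 0%.
- k = 2: all five observed gives +2/5 = +0.4 and 40% worse. Completers only (n = 3) gives 0.0 and 0%.

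If the exit criterion were applied to every such subject, no completer could show a Day 28 IGA above baseline unless the rise first appeared at Day 28.

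The other reading of the combined Day 28/EOS column keeps the subject in the summary. A Day 3 swab could then be reported as Day 28 engraftment, although sections 3 and 4.2 use how long the ratios stay above 40% to set later dosing frequency.

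**The case against.** The strongest reply is that the plan is milder than its list of exit criteria suggests, and most of that reply stands.

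- **Removal.** A reader might infer that reacting subjects are taken out of the study. The documents do not say so. The default in section 7.1 is to remain through Day 28, and exit for toxicity or worsening is worded as *may* or left to the investigator's judgement.
- **Safety follow-up.** A reader might infer that it stops at exit. It does not. Sections 8.2.1, 8.2.3 and 8.5 follow detected AEs to resolution or until judged permanent or stable, unscheduled visits are available, and the SAE window runs past Day 28 for any exit. What can be lost is scheduled assessments and late-arising non-serious AEs.
- **Escalation.** A subject who leaves with a DLT remains evaluable and is not replaced (section 5.5), so the 7-day count that governs Cohort 2 is protected.
- **Bias.** A reader might infer that worsened subjects drop out of the Day 28 results and that the product is flattered. The plan states no completers-only analysis. The EOS visit collects the same assessments, and individual trajectories are to be plotted, so in a cohort of five a worsened subject would be visible. Silence on labelling is shown; bias is not.
- **Persistence.** It would also go too far to say that the organism is still on the skin at 48H. Sections 3 and 4.2 themselves consider a fall below 40% by 6 hours.

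What the reply does not remove is that permissive wording leaves an unblinded investigator, who knows the outcome, to decide which subjects have Day 28 data.

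**Conclusion.** The point holds in a limited form. The protocol allows participation to end for a 1-point IGA rise, worsening acne or other toxicity when no intervention remains to be stopped, and it requires no Day 28 visit afterwards. For such a subject the possible loss is 21 to 27 study days of scheduled assessments and 14 to 20 days of recording of new non-serious AEs, for exits from Day 7 back to 6H. These ranges assume that the EOS visit falls on the exit day.

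The effect on the Day 28 IGA, lesion and engraftment summaries cannot be determined from the plan: worsened subjects may be omitted, or early values may be shown as Day 28. The shifts of 0.2 and 0.4 IGA grades are illustrations on assumed inputs, not estimates.

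Pregnancy raises a separate inconsistency. Section 7.1 lists it among reasons for which the investigator *may* discontinue a participant, whereas section 8.3 says "The study drug must be discontinued immediately (female subjects only and subject must be withdrawn from study". The two must be reconciled; this review takes no position on which should apply.

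**What to change.** 1. **Sections 7.1, 8.1 and 8.2.1.** Separate having no further study drug (not applicable after 0H) from the end of study participation. Ask dosed subjects with toxicity or worsening acne to attend the remaining scheduled visits through Day 28, unless consent is withdrawn or they are lost to follow-up. Treatment of any reaction stays with the clinician.
2. **Section 6.3.1.** Keep the assessment before other acne therapy as an additional visit. Record the start date of that therapy and flag values obtained after it.
3. **Section 10.4.** Tabulate early EOS values at their actual study day, not as Day 28, and report the number of subjects observed at each time point.
4. **Sections 7.1 and 8.3.** Reconcile the two statements on pregnancy.

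The cost is protocol wording plus a few visits that are already on the schedule. The downside is that IGA, lesion, biomarker and engraftment values obtained after other acne therapy must be read separately, so the gain is mainly in safety observation and only partly in the efficacy summaries.
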